Study Measures: Study measures are taken by clinical staff blinded to treatment condition at three timepoints: baseline, end of treatment (four months) and one-year follow-up.

Demographic Information: We will collect the following sociodemographic data: age, gender, educational attainment, race/ethnicity, smoking status, marital status, and health insurance status at baseline. These demographic measures will allow us to characterize the population.

CO level: Carbon Monoxide level (CO) will be collected using a coVita carbon monoxide measuring device. The participant will be required to breathe slowly through a cardboard tube to obtain this measurement. This measurement will quantify recent exposure to carbon monoxide (e.g. smoke/secondhand smoke/car exhaust/heater emissions).

Maximal Exercise Capacity: Maximal exercise capacity will be assessed on a treadmill using measurements of peak oxygen uptake, duration of treadmill exercise and maximal exercise intensity in METS. A continuous modified-Balke protocol will be used, with exercise increasing gradually at 1 MET increments at 2-minute intervals. Exercise is EKG monitored and stopped prior to exhaustion if the patient develops progressive angina, > 2mm ST segment depression, exercise induced hypertension (230 systolic, 105 diastolic), severe arrhythmias, dizziness or symptomatic hypotension. The occurrence of any concerning responses, other than high threshold angina, excludes a patient from the training protocol unless effective therapy is instituted. Patients will perform the maximal stress test taking their usual medications at a standardized time of day. The clinical staff at UVMMC have extensive experience

measuring peak exercise capacity in patients in the CR setting.¹²⁷ In lieu of a maximal stress test at CR exit, estimated METS while exercising on the treadmill may be used at the final CR session as a clinical measure of fitness at exit.

Socio-Cognitive Measures: We will assess current depressive symptoms (Beck Depression Inventory, BDI, Patient Health Questionnaire (PHQ-2)^{128,129} as well self-reported adaptive functioning and problems (ASEBA - Achenbach System of Empirically Based Assessment.¹³⁰ We will also assess self-reported social support (ISEL - Interpersonal support evaluation list).¹⁴⁷

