Quality of Life: The General Health Status M.O.S. SF-36 questionnaire will be administered with special attention to the physical function component score).^{131,132} Quality of life measures incorporate the EuroQual¹³³ and the disease specific MacNew Cardiac Health Status Questionnaire.^{134,135} These measures are all standardized and have adequate test-retest reliability.^{136,137}

Executive Function (EF): Several assessments will be administered to measure executive function, which has been shown to be important in characterizing how likely populations are to engage in various health behaviors.^{138,139} For initial characterization we will administer the Wechsler Abbreviated Scale of Intelligence (WASI),¹⁴⁰ and the Delis-Kaplan Executive Function System (D-KEFS).¹⁴¹ In addition, programmatic exercise has been shown to improve measures of executive function.¹⁴² To measure changes in these characteristics we will administer the following instruments/tasks at each assessment: Behavior Rating Inventory of Executive Function (BRIEF),¹⁴³ discounting of delayed hypothetical monetary rewards (Delay discounting, DD),¹⁴⁴ Time Perspective Questionnaire (TPQ),¹³⁹ digit span test (subset of the WASI), and Stop Signal Task (SST).^{145,146}

Treatment Access and Cost: To assess costs to participants (e.g. travel expenses, time spent, and out-of-pocket expenses), we will use a tool created for our prior study that adapted the Client Drug Abuse Treatment Cost Analysis Program (DATCAP; www.datcap.com/client.htm) for use in cardiac rehabilitation. Direct nonmedical and indirect costs include the value of time of participants attending the program, waiting, traveling, or exercising, as well as transportation expenses.

Physical Activity: We will be utilizing a portion of the IPAQ (International Physical Activity Questionnaire) at one-year follow up.

Procedures by condition:

Usual care: Participants in usual care will come in for the scheduled assessments but will not receive other interventions.

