If the CR clinics (UVMMC, Copley Hospital, Northwestern Medical Center) cease in-person visits, session completion will be calculated by tracking remote participation. Study participants across arms will be expected to complete two CR sessions per week. One session will consist of completing the weekly telemedicine call conducted by CR staff and one session will consist of completing a recommended step goal for that day, as confirmed by an Omron pedometer. A session will be coded as missed (excused or unexcused, depending on the situation) if a participant fails to send a step count or fails to complete the telemedicine call from the CR case manager.

For research involving survey, questionnaires, etc.: Describe the setting and the mode of administering the instrument and the provisions for maintaining privacy and confidentiality. Include the duration, intervals of administration, and overall length of participation. (describe and attach all instruments)

Not applicable

Questionnaires will be administered at intake, after 4 months, and at one year. All questionnaires will be administered in a private setting at the Cardiac Rehabilitation Facility. Questionnaires should take approximately one hour to complete.

As listed above the following questionnaires will be administered (and are attached):

Beck Depression Inventory. Note: the BDI includes a question about suicidal thoughts. If a subject endorses this item research staff will follow the attached suicidality protocol.

MacNew Cardiac Health Status Questionnaire

TCAP

Interpersonal Support Evaluation List

International Physical Activity Questionnaire (IPAQ, brief form)

Executive Function Battery Questionnaires:

The Time Perspective Questionnaire – Exercise (TPQ)

Euroqol (Quality of Life)

Achenbach System of Empirically Based Assessments (ASEBA) – Adult Self Report or Older Adult Self Report

Behavior Rating Inventory of Executive Function (BRIEF)

Data Collection: Questionnaire Administration Amidst Contact Restrictions (e.g. COVID-19)

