Whenever possible, paper questionnaires will be completed remotely, either by mail (completed and returned by the study participant) or with the researcher over the phone. If in-person research visits are not allowed the following assessments will not be collected: IQ test (WASI), Stop Signal Task (SST), Delay Discounting Task (DD), Trail Making Task (TMT), Digit Span Task. If in-person research visits are allowable these assessments will be completed using appropriate distancing measures and PPE as is outlined in our approved lab safety reopening plan (attached).

Statistical Considerations: *Delineate the precise outcomes to be measured and analyzed. Describe how these results will be measured and statistically analyzed. Delineate methods used to estimate the required number of subjects. Describe power calculations if the study involves comparisons. Perform this analysis on each of the primary and secondary objectives, if possible.*

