By definition, primary outcome data will not be missing since it focuses on program participation. For other variables, minor amounts of missing data, due to factors other than dropout from the CR program, will be ignored, leading to deletion of cases in regression analyses. However, if substantial amounts of missing data of key predictor variables exist, we will explore the randomness of missing data using Little's MCAR (missing completely at random) test in SPSS 24. If we cannot reject the null hypothesis, we will proceed to use multiple imputation procedures in SAS 9.4 (PROC MI and PROC MIANALYZE) to generate results based on imputed data.

Although this study is powered for our primary outcome of adherence to CR, we will also carefully examine improvements in fitness, and other health outcomes (quality of life, maximal exercise capacity, weight, waist measurements) between conditions, using the pre-planned comparisons outlined for the primary outcome. Additionally, we will examine changes in executive function measures and socio-cognitive status at 4 and 12 months. Changes in these scores will also be examined for possible gender interactions. Since multiple observations for each participant will be obtained, the general analytic approach will consist of analysis of covariance (ANCOVA) at 4 months and repeated measures analysis of variance (ANOVA) at 12 months. Formal testing will examine the condition by time interaction term to assess differential time changes between treatment conditions. Post-hoc comparisons between conditions will be made if significant interactions are observed.

Survival analyses will be conducted once all participants have completed the 36 sessions of their CR program (or, alternatively, have dropped out of the program). Preliminary analyses of all other outcome measures will occur upon collection of all 4-month measures across all participants. Final analyses of secondary outcome measures, using repeated measures procedures, will be conducted upon collection of all 12- month measures across all participants. Across all tests, statistical significance will be defined as $p < 0.05$ (2-tailed).

Cost Effectiveness Analyses

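### The task-based executive-function measures stop when in-person visits are barred, but the 12-month repeated measures ANOVA has no stated way to keep participants who miss a visit

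*Combined protocol and SAP*

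**What the plan says.** The protocol's Study Design section names improvement in executive function as a secondary outcome, over four months and at one year. Study Measures sets "three timepoints: baseline, end of treatment (four months) and one-year follow-up". Its Executive Function paragraph states "To measure changes in these characteristics we will administer the following instruments/tasks at each assessment" and names five: two self-report forms (BRIEF and the Time Perspective Questionnaire) and three tasks (delay discounting, digit span, stop signal).

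The protocol section on questionnaire administration under contact restrictions says "If in-person research visits are not allowed the following assessments will not be collected" and lists "IQ test (WASI), Stop Signal Task (SST), Delay Discounting Task (DD), Trail Making Task (TMT), Digit Span Task". Paper questionnaires continue, where possible, by mail or phone.

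The protocol's Data Analysis section and the SAP's Primary and Secondary Data Analyses both specify "analysis of covariance (ANCOVA) at 4 months and repeated measures analysis of variance (ANOVA) at 12 months", with the condition-by-time interaction as the formal test. On missing data other than the primary outcome, the SAP says that minor amounts "due to factors other than dropout from the CR program, will be ignored, leading to deletion of cases in regression analyses". If substantial data are missing on key predictor variables, Little's test is run, and multiple imputation follows if that test does not reject.

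**The concern.** The restriction rule was written into data collection but not carried into the analysis. During a closure, executive-function change is measured by self-report alone. The tasks are missing for whoever happens to be due a visit, and different participants lose different visits. A repeated measures ANOVA that needs all three visits would then drop people who still have one or two valid assessments.

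Such loss is set by the calendar, not by the participant's condition. The retained visits are sound data, and deleting them costs precision without reducing bias. The SAP says the study is powered for adherence and states no power for these secondary outcomes, so there is no known margin to absorb the loss.

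**Working it through.** **The plan's own figures.** The documents give no missing-visit rate, complete-case number or power for executive function. The nearest figure that can be checked is the primary sample size: 54% against 28%, likelihood ratio test, two-sided 0.05. Power is 80.4% at 56 per condition (the SAP's number) and 81.1% at 57 (the protocol's), and 3 × 57 + 38 = 209. This only fixes the starting numbers.

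**Which measures are lost.** Setting the two lists side by side, delay discounting, digit span and stop signal are on the not-collected list (3 of 3 tasks). BRIEF and the Time Perspective Questionnaire are kept (2 of 2 self-report forms).

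**Assumptions, none of them in the documents.** Enrolment is uniform over a window of R = 36, 48 or 60 months. There is one closure of L = 3, 6 or 12 months starting at mid-window. No other visits are missed.

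**Share lost.** With visits at 0, 4 and 12 months:

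- Enrolment continues: share missing the 12-month visit = L/R. Share missing any visit = [L + min(L, 4) + min(L, 8)]/R.
- Enrolment pauses for the closure, so no baseline is missed: share missing the 12-month visit = L/(R − L). Share missing any visit = [L + min(L, 4) − max(0, L − 8)]/(R − L).

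For R = 48 and L = 6, continuing: 6/48 = 12.5% and (6 + 4 + 6)/48 = 33.3%, a ratio of 2.67. Complete cases fall from 209 to about 139, and arms of 57 and 38 fall to about 38 and 25. With a pause: 6/42 = 14.3% and 10/42 = 23.8%, a ratio of 1.67, leaving about 159.

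**Standard error.** The contrast is the between-arm difference in change from baseline to 12 months, with equal variances and a common within-person correlation ρ of 0.5 or 0.7. Complete-case variance is proportional to 2(1 − ρ) divided by the complete share. The all-visits variance comes from generalised least squares, summing the information from every observed-visit pattern.

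A partial check by hand for R = 48, L = 6, continuing: 32/48 have all three visits and 4/48 miss only month 4. Keeping that second group alone gives √(36/32) = 1.06. Using the remaining partial records as well raises the ratio to 1.11 to 1.12.

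| R, L (months) | Continuing: miss month 12 / any visit / ratio | SE excess | Paused: miss month 12 / any visit / ratio | SE excess |
|---|---|---|---|---|
| 36, 3 | 8.3% / 25.0% / 3.0 | 9% | 9.1% / 18.2% / 2.0 | 7% |
| 36, 6 | 16.7% / 44.4% / 2.67 | 17–18% | 20.0% / 33.3% / 1.67 | 13% |
| 36, 12 | 33.3% / 66.7% / 2.0 | 20–26% | 50.0% / 50.0% / 1.0 | 7–9% |
| 48, 3 | 6.3% / 18.8% / 3.0 | 6% | 6.7% / 13.3% / 2.0 | 5% |
| 48, 6 | 12.5% / 33.3% / 2.67 | 11–12% | 14.3% / 23.8% / 1.67 | 8–9% |
| 48, 12 | 25.0% / 50.0% / 2.0 | 10–14% | 33.3% / 33.3% / 1.0 | 5–6% |
| 60, 3 | 5.0% / 15.0% / 3.0 | 5% | 5.3% / 10.5% / 2.0 | 4% |
| 60, 6 | 10.0% / 26.7% / 2.67 | 8–9% | 11.1% / 18.5% / 1.67 | 6% |
| 60, 12 | 20.0% / 40.0% / 2.0 | 7–9% | 25.0% / 25.0% / 1.0 | 3–4% |

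The table uses expected shares. With random enrolment draws in arms of 57 and 38, the worst case rises slightly, to 27–28%. The overall range is therefore about 3% to 28%.

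**The case against.** Five points can fairly be made against this.

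- **The complete-case form is inferred.** Neither analysis section states listwise deletion or says that all three visits must be present. This stands as a caution. It is nevertheless the usual form of the named method, and the only deletion rule in the SAP points the same way.
- **The SAP is not silent on missing data.** A reader might infer that nothing applies, but the imputation route exists, and calendar-driven loss would often pass Little's test. Its trigger is missing predictors, however, and these are outcomes. The text also gives no alternative if the test rejects.
- **The multiple of two to three is not a fact about this trial.** It requires enrolment to go on through the closure. Phone and electronic consent make that possible, but the documents do not say it would happen. With a pause the multiple is 1 to 2, and it approaches 1 if the same people miss every visit. It also counts anyone with a missed visit. For a 12-month closure with enrolment continuing, those missing exactly one visit only equal the share missing month 12.
- **Questionnaire mode.** The protocol says "All questionnaires will be administered in a private setting at the Cardiac Rehabilitation Facility", and restrictions move the forms to mail or phone. A reader might infer biased treatment comparisons and want mode as a covariate. The documents do not support that. Allocation is concurrent in stratified blocks, so a calendar-driven shift should largely cancel in the condition-by-time test. Mode is also post-randomisation and confounded with the restriction period.
- **The stakes are limited.** These are secondary outcomes, and the 4-month ANCOVA does not need the 12-month visit. Both statements are correct.

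**Conclusion.** The concern holds as a gap between the data-collection rule and the analysis. All three task-based change measures stop when in-person visits are barred, and the stated 12-month method has no clear provision for the resulting missing outcomes. The harm shown is lost precision. No bias in the treatment comparison has been demonstrated.

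Under the assumed closures the standard error penalty is about 3% to 28%. For 48 months of enrolment and a 6-month closure it is 8–9% with a pause and 11–12% without. These figures rest on assumed dates, a common correlation of 0.5 to 0.7, loss driven only by the calendar, and the complete-case reading of the ANOVA. Executive function as a whole is not lost, because two self-report forms continue. The change is worth making because it is better in every scenario examined and costs little.

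**What to change.** In the protocol's Data Analysis section and the SAP's Primary and Secondary Data Analyses, replace the repeated measures ANOVA for the 4- and 12-month secondary outcomes with a likelihood-based mixed model containing condition, time and condition by time. State that baseline, 4-month and 12-month values all enter as outcomes, so that a participant missing any one visit, including baseline, contributes the others. The planned contrasts at each time come from this model.

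Report, by visit and arm, how many of each task were not collected because of restrictions. Questionnaire mode (facility, mail, phone) may be recorded and examined in a sensitivity analysis, but it should stay out of the main model.

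The cost is a few sentences of SAP text, routine model code, a reason code for uncollected tasks and, if wanted, one mode field per questionnaire. No visit, procedure or sample size changes.

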Power: Sample sizes were calculated to provide sufficient power to calculate differences in our primary outcome (CR adherence, as measured by % completing 30+ sessions) between the control condition and any of the three intervention conditions as well as between the combined intervention and either of the interventions delivered alone. Of most relevance, preliminary data from a previous trial on the use of incentives to increase CR rates among lower-SES individuals show that 54% of those receiving incentives completed the 30+ sessions compared to 28% of those receiving usual care. Using these proportions and the likelihood ratio test for two proportions in SAS POWER, 57 individuals per condition would be needed to detect a significant difference between conditions with 80% power. A seminal set of studies, conducted by Co-I [name], that systematically determined the efficacy of case management and incentives, alone and in combination, on cocaine abstinence, provided additional data for the power estimates.⁵⁴⁻⁵⁸ Using effect sizes from these five studies, the maximum estimated number of participants needed per condition is 50 to detect a significant difference in treatment adherence in combined intervention vs. single intervention with 80% power. Comparing any of the interventions singly or combined to usual care at four months post-treatment is estimated to require at most 25 participants per condition. Supporting these estimates, additional studies on the use of case management or incentives for adherence to other health-related behaviors have demonstrated effect sizes comparable to the studies referenced above.^{66,67,73,106,107} As such, the proposed sample size of 209 randomized subjects (57/intervention condition, 38 control) will allow us to conduct all pre-planned pairwise comparisons of the primary outcome measure (program adherence) with 80% power.

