Data Analysis: Treatment conditions will be compared for differences in baseline demographic characteristics using one-way Analysis of Variance (ANOVA) (or a nonparametric alternative, such as the Kruskal-Wallis Test) for continuous measures and chi-square tests (or Fisher's Exact Test) for categorical variables. If specific characteristics differ significantly across treatment conditions and are predictive of treatment outcomes, they will be considered as covariates in subsequent analyses. Primary analyses will include all subjects randomized to treatment conditions independent of early dropout or non-adherence, consistent with an intent-to-treat approach for randomized clinical trials.¹⁴⁷

The primary outcome measure in this trial will be CR adherence (% completing 30+ sessions) compared between the control condition and any of the three intervention conditions as well as between the combined intervention and either of the interventions delivered alone. Proportions completing all CR sessions will be examined across conditions using the test for differences between two population proportions (z), with 95% confidence intervals on effect sizes. To look at other measures of attendance, Cox proportional hazard models will be used to test differences in number of CR sessions completed

(i.e., time to dropout) between conditions. Purposeful selection of covariates will be used to build models.¹⁶⁴ Once final models have been derived, we will generate estimated hazard ratios with 95% confidence intervals and graphs of covariate-adjusted survival functions. Across all tests, statistical significance will be defined as $p < 0.05$ (2-tailed).

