A seminal set of studies, conducted by a member of our research team (Co-I [name]), that systematically determined the efficacy of case management and incentives, alone and in combination, provided additional data for the power estimates. This set of studies, conducted in the 1990's and early 2000's compared treatment conditions in programs for achieving cocaine abstinence among individuals with cocaine dependency.⁵⁴⁻⁵⁸ Although the primary outcome variable of these studies – cocaine abstinence, either continuously or at selected time points – differs from this study's focus on CR attendance, they are similar in terms of providing case management services, with or without incentives, to demographically comparable individuals to boost their EF, improving adherence to a program attempting to change behavior, and thereby instill long-term health benefits. Two of these earlier studies^{56,57} compared the effects of a community reinforcement approach (i.e., case management) with incentives to usual care in achieving continuous cocaine abstinence at the end of four to 16 weeks of treatment. The third study⁵⁴ tested the effects of the addition of incentives vs. usual care. Using condition proportions who achieved continuous cocaine abstinence at these time periods and the likelihood ratio test for two proportions in SAS POWER, we calculate sample size of each treatment condition vs. usual care required a maximum of 25 participants to achieve 80% power.

Subsequent studies examined initial cocaine abstinence among individuals with cocaine dependence comparing case management with and without incentives, case management with contingent incentives versus case management with non-contingent incentives, and case management with incentives versus incentives only.^{58,161,162} Across all of these permutations of combined intervention vs. single intervention, the maximum number of participants needed per condition to detect a significant difference between incentives or case management alone vs incentives and case management in combination in treatment adherence with 80% power was 50, again using the likelihood ratio test for two proportions in SAS POWER.

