In the literature, studies on the use of case management or incentives for adherence to other health-related behaviors have demonstrated effect sizes comparable to the studies referenced earlier,^{66,67,106,107} providing additional evidence that those prior studies are appropriate for estimating sample sizes for the proposed study. Thus, we estimate that 57 participants per treatment condition (i.e., case management only, incentives only, and case management with incentives) and 38 participants in the usual care condition will allow us to conduct all pre-planned pairwise comparisons of the primary outcome measure (program adherence) with 80% power.

Randomization

Stratified random allocation of participants will be used to assign individuals to conditions, using two dichotomous variables to stratify the sample: age (<57 years of age vs. ≥ 57) and smoking status (current smoker vs. former/non-smoker). Age and current smoking were the two demographic variables which significantly predicted CR attendance in the prior trial. As median age in our prior trial was 57, and 40% of participants were current smokers, stratifying using the proposed cut-offs will result in randomization cell sizes of appropriate size. Participants will be allocated to conditions using a 3:3:3:2 routine, whereby for every three individuals assigned to one of the three treatment conditions (case management only, incentives only, and case management plus incentives), two individuals will be assigned to the control condition (usual care). Assignment of participants to conditions will be conducted using the stratified block design method¹⁶³ in the

Interactive Voice Recognition (IVR) system maintained by the Medical Biostatistics Unit at the University of Vermont. Using this system will allow us to allocate participants over time, as they become eligible, while still maintaining desired arm counts across conditions.

Primary and Secondary Data Analyses

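### The 25-per-condition figure has no stated numerical basis for case management alone versus usual care, and 80% power for every pairwise comparison does not follow from the plan's own cardiac rehabilitation rates

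*Combined protocol and SAP*

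**What the plan says.** The comparison of each intervention arm with usual care on the primary outcome, "CR adherence, as measured by % completing 30+ sessions" in the protocol, is pre-planned. Case management alone versus usual care is one of these contrasts.

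The Power paragraph (protocol, Statistical Considerations) gives two sample sizes for comparisons with usual care:

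- From the earlier cardiac rehabilitation trial, "54% of those receiving incentives completed the 30+ sessions compared to 28% of those receiving usual care", so that "57 individuals per condition would be needed to detect a significant difference between conditions with 80% power". The SAP, under Sample Size and Power, gives 56 from the same two percentages, there attached to 36 sessions.
- From cocaine-treatment studies, a comparison of "any of the interventions singly or combined to usual care at four months post-treatment is estimated to require at most 25 participants per condition".

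The SAP describes the studies behind the second figure. Two of them "compared the effects of a community reinforcement approach (i.e., case management) with incentives to usual care in achieving continuous cocaine abstinence", and a third tested the addition of incentives against usual care. From these, "we calculate sample size of each treatment condition vs. usual care required a maximum of 25 participants to achieve 80% power". In the later studies that the SAP lists for the combination-versus-single contrasts, case management without incentives appears only as a comparator for a combined treatment.

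Both documents conclude that 57 per intervention arm and 38 in usual care "will allow us to conduct all pre-planned pairwise comparisons of the primary outcome measure (program adherence) with 80% power".

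**The concern.** The protocol applies the 25 to interventions given singly, and the SAP applies it to each treatment condition. The listed sources cover the combination and incentives but not case management alone. Nor is there a case-management completion rate anywhere else in the plan from which power for that contrast could be worked out.

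The same paragraph also holds two incompatible figures for one single intervention. Incentives versus usual care needs 57 per condition on the outcome of this trial, yet any single intervention is said to need at most 25.

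At stake is how a result will be read. If case management alone does not differ significantly from usual care, a stated 80% power invites the inference that it does not work. The plan does not state that inference, but the power claim lends it support that the plan's inputs do not supply.

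**Working it through.** **Inputs.** Usual care 28% and incentives 54% (protocol, Power; SAP, Sample Size and Power). Two-sided 0.05. Arms of 57 and 38. Sizing by the likelihood ratio test for two proportions; analysis by the two-proportion z test. No completion rate for case management alone is given, so every such rate below is an assumption.

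**Formulas.** Likelihood ratio (LR): power = P(χ²₁(λ) > 3.841), with λ = 2N[w₁f(p₁) + w₂f(p₂) − f(p̄)], f(p) = p ln p + (1−p) ln(1−p), w the allocation fractions and p̄ = w₁p₁ + w₂p₂. The z approximation: power = Φ[(|p₂−p₁| − 1.96·s₀)/s₁], with s₀ the pooled and s₁ the unpooled standard error. Exact power sums the binomial probabilities of all outcomes in which the z test rejects.

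**1. The plan's own figure.** For 28% versus 54% at 1:1, λ per participant is 0.0708. With 56 per arm, λ = 112 × 0.0708 = 7.93 and power is 80.4%; with 55 it is 79.7%. So n = 56, which matches the SAP exactly and the protocol's 57 to within one per arm.

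**2. The same rates with 25 per arm.**
- LR: λ = 50 × 0.0708 = 3.54, power 46.9%.
- z: p̄ = 0.41, s₀ = √(0.41 × 0.59 × 2/25) = 0.139, s₁ = √((0.28 × 0.72 + 0.54 × 0.46)/25) = 0.134; (0.26 − 1.96 × 0.139)/0.134 = −0.09, power 46.2%.
- Exact: 50.6%.

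From 28%, 25 per arm gives 80% power only at about 67% completion (LR), a gain of 39 points. The 25 itself cannot be reproduced, because the abstinence proportions behind it are not stated. For assumed control rates of 5% to 20% it implies differences of about 30 to 38 points.

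**3. The planned 57 versus 38 at 54% versus 28%.** p̄ = (38 × 0.28 + 57 × 0.54)/95 = 0.436; s₀ = 0.104, s₁ = 0.098; (0.26 − 1.96 × 0.104)/0.098 = 0.57, power 71.7%. LR gives 71.7% and exact 71.6%.

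**4. Completion rate needed for 80% power, from 28% (LR).**
- 57 versus 38: about 57%, a gain of 29 points against the 26 points (54 − 28) seen with incentives.
- 57 versus 57: about 54%.

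The three points between these thresholds are due to the allocation.

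**5. Case management alone at 57 versus 38, usual care 28% (exact).**

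| Assumed completion | Power |
|---|---|
| 38% | 17% |
| 43% | 32% |
| 48% | 50% |
| 53% | 68% |
| 54% | 72% |
| 57% | 81% |

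**The case against.** Four points can be made for the plan.

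**Case management does have cited support.** Section 1.G says it works as a single treatment, the Power paragraph says the cocaine studies examined each component alone as well as together, and both documents point to further studies with comparable effects. A reader might infer that the contrast has no basis at all, and that is too strong. What stands is narrower: none of this support comes with a rate or a derived sample size, and the studies the SAP describes behind the 25 do not contain the contrast.

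**Two sources may yield two sample sizes.** The 57 comes from incentives in cardiac rehabilitation and the 25 from cocaine abstinence, and the intervention arms were set at the larger figure. The 57 says nothing direct about case management. This is right, and the conflict is only with the blanket statement that any single intervention needs at most 25. The SAP also acknowledges the difference in outcome and argues for relevance, so the mismatch is not concealed.

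**Low power has not been shown.** A reader might infer from the table that the case-management contrast is underpowered. The documents do not support that, because they give no case-management rate. Section 1.F reports improvements of 10 to 25% for other approaches, but these concern enrolment and mostly different interventions, so they cannot fix a completion rate. Power is undetermined. Nor should the 57% threshold be put down wholly to the missing source, since part of it is the allocation.

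**Confidence intervals are already planned.** They are, which makes the interpretive part of the fix easy. The 80% statement would still be wrong as written.

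**Conclusion.** The concern holds in this limited form. The 25 has no stated numerical basis for case management alone versus usual care, and it conflicts with the plan's 56 to 57 per condition for incentives on the outcome of this trial, where 25 per arm would give about 46 to 51% power. The claim of 80% power for all pairwise comparisons is not met on the only cardiac rehabilitation rates in the plan: incentives versus usual care has about 72% at 57 versus 38. For case management alone, 80% is reached only at about 57% completion or more.

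These figures assume 28% under usual care, a two-sided 0.05 level and the planned arm sizes. The combination-versus-single contrasts rest on a separate figure of 50 per condition and are not judged here. This is an error in what the plan claims for its power. It does not invalidate the design or the planned tests.

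**What to change.** In the protocol's Power paragraph and the SAP's Sample Size and Power section:

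- Withdraw the 25 as support for the usual-care contrasts on this outcome.
- Replace the blanket 80% sentence with power at the actual 57 versus 38. For incentives versus usual care, state about 72% at 54% versus 28%.
- For case management alone, say that no rate against usual care was available and tabulate power over a stated range of completion rates, for example 38% to 57% (about 17% to 81%). Label the rates as assumptions and note that 80% is reached only at about 57% or more.
- State that a non-significant case management versus usual care result will be interpreted from the 95% confidence interval already planned, and not as evidence of no effect.

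This is rewording only and does not alter enrolment. The cost is a less favourable stated power.
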